A “related AE” in VA research is an AE or problem that may reasonably be regarded as caused by, or probably caused by, the research procedures [VHA Handbook 1058.01 (4.r)] AEs will be categorized according to the likelihood that they are related to the study intervention according to VAPSHCS IRB protocol. Specifically, they will be labeled probably not related, possibly related, and probably related to the study intervention.

3d. AE Reporting and Follow-up

Each participant will have an adverse events form created and completed during participation. Each AE will be recorded on this particular form that records the subject’s code number, date of AE, severity, attribution level to study, action taken and outcome.

In addition, research staff will record all AEs using a standard VAPSHCS approved Adverse Event Reporting Log that records the subject’s code number, date of AE, severity, attribution level to study, action taken and outcome.

These adverse events will be provided annually in this format to the DSMC, both the VAPSHCS and UW IRBs and NCCIH in accordance with requirements. If the event is related to the sleep sub-study, it will also be reported to the WSU IRB.

3e. SAE Reporting

SAEs that are unanticipated, serious, and possibly related to the study intervention will be reported to the chair of the DSMC, both the VAPSHCS and UW IRBs and NCCIH in accordance with requirements. If the event is related to the sleep sub-study, it will also be reported to the WSU IRB.

- Unanticipated fatal or life-threatening SAEs related to study procedures will be reported immediately to the VA HRPP (orally), NCCIH Program Officer, chair of the DSMC and the UW and VAPSHCS IRBs.
- Other serious and unanticipated SAEs related to study procedures will be reported to the NCCIH Program Official, DSMC chair and to the VAPSHCS IRB within 5 days, and to the UW IRB within 10 days.

Anticipated or unrelated SAEs will be reported to the DSMC and NCCIH Program Officer as part of the annual DSM report. These SAEs will also be reported to the VAPSHCS IRB as part of the annual VAPSHCS IRB status report. The UW IRB does not require reporting SAEs that are not related to study procedures.

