Research staff will record all SAEs using a standard form that records the subject’s code number, date of SAE, severity, attribution level to study, action taken and outcome. These adverse events will be provided annually in this format to the DSMC, both the VAPSHCS and UW IRBs and NCCIH in accordance with requirements.

The Chair of the DSMC will be contacted when an SAE is discovered to receive consultation on the matter. The Chair of the DSMC will use her discretion to determine whether the other DSMC members should also provide additional consultation.

3f. Data Quality Assurance and Monitoring

Description of Plan for Data Quality and Management

The research manager and study staff will review all data collection forms on an ongoing basis for data completeness and accuracy as well as protocol compliance. Data verification will take place in the form of double-data entry. Specifically, two separate study staff members will enter data from the hard copy forms into the database to ensure accuracy of data entry. Visual Basic for Applications (VBA) code inserted in the Microsoft Access database will verify the 2nd entry against the 1st entry. Any discrepancies between the two entries will cause a warning window to open informing the data operator that a discrepancy has been detected.

All data entry discrepancies between these two data entries will be solved by the staff member completing the 2nd portion of double entry.

Exploratory data collected during the treatment sessions will be singly entered into the Treatment Database. For quality control, a second unblinded staff member will review 10% of the treatment data at the completion of the study. If there is more than a 5% error rate, then Investigators will be notified to determine a plan of action which may include implementing a 2nd entry verification.

All group treatment sessions will be audio recorded to ensure compliance to treatment procedures. A portion of treatment sessions will be randomly selected to be reviewed by study researchers to ascertain fidelity to protocol. Study clinicians will receive feedback as needed if they diverge from protocol.

In addition, research study staff will review the study data in detail on a quarterly basis to detect any systematic issues with data collection.

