This study will be stopped prior to its completion if: (1) one of the interventions is associated with adverse effects that call into question the safety of the intervention; (2) any new information becomes available during the trial that necessitates stopping the trial; or (3) other situations occur that might warrant stopping the trial.

3i. Designation of a Monitoring Committee

Name/Role*	Credentials	Organization	Expertise
[name]	Ph.D.	Independent Consultant	Biostatistician
[name]	Ph.D.	VAPSHCS	Staff Psychologist
[name]	Ph.D.	VAPSHCS	Clinical Psychologist, Behavioral Interventions/Clinical Trials

The Data Safety Monitoring Committee (DSMC) for this study is comprised of Drs. [name] (chair), [name] and [name]. [name], an independent consultant, has no professional or personal connection with the co-PIs.

Although [name] is employed at the VAPSHCS, she does not collaborate with any of the research team members in a research or clinical capacity on a regular basis. Likewise, although [name] is employed at the VAPSHCS, she does not collaborate with the Co-PIs in a research or clinical capacity on a regular basis.

Drs. [name] and [name] are qualified to review the patient safety data generated by this study because of their unique expertise in the area of randomized controlled trials (RCT) examining the efficacy of psychological interventions in Veteran populations. [name] was selected given his/her expertise in biostatistics.

3j. Methods and Timing for Assessing Recording, and Analyzing Safety Parameters

Monitoring Subject Safety and Study Compliance

Study researchers including staff members and study clinicians who conduct the telephone assessments, brain wave activity assessments, cognitive assessments, and facilitate the treatment groups will collect safety information on an ongoing basis. By systematically monitoring for events, we will ensure that problems are detected immediately and addressed as indicated.

Brain Wave Activity Assessments

The research staff member conducting the assessment will ask each participant following completion of the assessment whether they experienced any negative effects during the assessment they associate with the study procedures. The response to this question will be captured using the EEG Assessment Recording Sheets.

Treatment

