Each quarter research staff will generate the same study report that outlines study progress including recruitment, retention/attrition, any protocol deviation or violation that warrants a note-to-file, and AEs, SAEs and unanticipated problems for that particular quarter. This report will be provided to the Co-PIs and the chair of the DSMC. The chair of the DSMC may solicit input from the other DSMC members if she detects anything of concern (e.g. higher rates of AEs than anticipated). The Chair of the DSMC will generate a report if there is anything of concern that will be supplied to the study PIs, VAPSHCS and UW IRBs and NCCIH.

Annual Report

Study staff will also generate an Annual Report that will include a list and summary of any protocol deviation or violation that warrants a note-to-file, and AEs, SAEs and unanticipated problems. In addition, the Annual Report will address (1) whether AE rates are consistent with pre-study assumptions; (2) reason for dropouts from the study; (3) whether all participants met entry criteria; (4) whether continuation of the study is justified on the basis that additional data are needed to accomplish the stated aims of the study; and (5) conditions whereby the study might be terminated prematurely.

The Annual Report will be sent to all members of the DSMC. The DSMC along with the Co-PIs will convene to review and discuss the report. The annual progress report will be forwarded to (1) the VAPSHCS IRB, (2) the UW IRB and (3) NCCIH.

3k. Study Report Outline for the Independent Monitors(s) (Interim or Annual Reports)

The study team will generate progress reports on a quarterly basis for review by the Chair of the DSMC, as well as an annual report to be reviewed by all DSMC members.

Study Report Outline for Progress Reports

- I. Table of Contents
- II. Introduction
 - A. Summary of Study Status and Issues or Problems
- III. Study Administration
 - A. Recruitment Status
 - i. Enrollment by Month/Quarter
 - ii. Comparison of Targeted to Actual Enrollment
 - B. Retention Status
 - i. Overall Subject Status
 - ii. Individual Subject Status
- IV. Study Data Reports/Tables or Figures
 - A. General Information
 - i. Enrollment

- ii. Demographic/Baseline Data
- iii. Subject Status
- B. Safety Assessment
 - i. Treatment Duration for All Subjects
 - ii. AE Data
 - a. Overall Listing
 - b. Specific Symptom Listing
 - c. SAE Listing
 - d. Subject Deaths

Study Report Outline for Annual Reports

- I. Table of Contents

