- II. Introduction
 - A. Summary of Study Status and Issues or Problems
 - B. Report Preparation Procedures
- III. Study Description
 - A. Project Organization Chart, Personnel
 - B. Brief Statement of Purpose of Trial
 - C. Projected Timetable and Schedule
- IV. Study Administration
 - A. Recruitment Status
 - i. Enrollment by Year/Month
 - ii. Comparison of Targeted to Actual Enrollment
 - B. Retention Status
 - i. Overall Subject Status
 - ii. Individual Subject Status
- V. Study Data Reports/Tables or Figures
 - A. General Information
 - i. Enrollment
 - ii. Demographic/Baseline Data
 - iii. Subject Status
 - B. Safety Assessment
 - i. Treatment Duration for All Subjects
 - ii. AE Data
 - a. Overall Listing
 - b. Specific Symptom Listing
 - c. SAE Listing
 - d. Subject Deaths

Study Report tables will be generated only from aggregate (not by group assignment) baseline and aggregate safety data for the study population.

3I. Reporting Changes in Study Status

During the funding of this study, any action by an IRB, the DSMC, or one of the study investigators that results in a temporary or permanent suspension of the study will be reported to the NCCIH Program Official within 1 business day of notification.

4. Potential Benefits of Research to Participants and Others

Previous studies with the two treatments (HYP and MM) that will be examined support their efficacy reducing pain. We anticipate based on this previous research that many of the participants will experience significant reductions in their daily pain and other benefits

associated with the treatments. Although we do not anticipate that the education control condition will result in any improvements in the outcome variables studied, previous participants report high levels of satisfaction with this condition, and report that they find the information useful.

To increase the chances that those participants assigned to the control condition will get the most benefits possible out of their participation, they will all be invited to receive one of the two active treatments (their choice) after they complete their final follow-up assessment. In addition, we anticipate that some of the participants who are initially randomized to one of the active treatments will not benefit from that treatment, and that this may be related to their baseline EEG. Thus, even those who received one of the active treatments will be invited to participate in the other treatment they did not receive.

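### The stopping criterion concerns one intervention, but the monitoring committee has no documented way to compare adverse event rates between arms

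*Combined protocol and SAP*

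**What the plan says.** Section 3h (Study Discontinuation) gives as its first ground for stopping that "one of the interventions is associated with adverse effects that call into question the safety of the intervention". It names no deciding body and no numerical threshold.

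Section 3k sets the content of the reports for the independent monitors. On frequency: "The study team will generate progress reports on a quarterly basis for review by the Chair of the DSMC"; an annual report goes to all members. On content: "Study Report tables will be generated only from aggregate (not by group assignment) baseline and aggregate safety data for the study population". The report outlines also include AE and SAE listings.

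Sections 3d and 3e describe the event records supplied annually to the DSMC. The AE form and log hold "code number, date of AE, severity, attribution level to study, action taken and outcome"; the SAE form has the corresponding fields. Under 3c, events are "labeled probably not related, possibly related, and probably related to the study intervention", without saying which of the three interventions is meant. Section 3e adds a route for single events: "The Chair of the DSMC will be contacted when an SAE is discovered to receive consultation on the matter".

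Under 3j the annual report must address "whether AE rates are consistent with pre-study assumptions", and the DSMC and the Co-PIs meet together to discuss it.

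**The concern.** Criterion (1) calls for a judgement about a single intervention, and rates are naturally judged against the other arms. Section 3k removes group assignment from the tables in which such a comparison would be made, and nothing else in the documents puts it back.

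The protocol itself expects harms to differ by arm. Section E1c lists distressing memories under hypnosis and disorientation or grogginess under hypnosis or mindfulness, and anticipates no stress or discomfort from education. An excess in one active arm is the situation criterion (1) appears to be written for. In a pooled table that excess is averaged with two other arms and cannot be traced to its source. What is at stake is how quickly, and how reliably, an arm-specific safety problem would be recognised.

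**Working it through.** **1. The texts side by side.** The documents give no safety boundary and no expected AE rate, so there is no figure of the plan's own to reproduce.

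| Information reaching the DSMC | Section | Arm shown? |
|---|---|---|
| Quarterly and annual report tables | 3k | No, excluded explicitly |
| AE and SAE records and listings | 3d, 3e, 3k | No arm field listed |
| Attribution category | 3c | Intervention not specified |
| Consultation with the chair on an SAE | 3e | No disclosure or unmasking step stated |
| AE rates against pre-study assumptions | 3j | Overall rate; no reference rate in the documents |

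No closed report, coded-arm table or procedure for requesting assignments appears.

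**2. A pooled count does not identify an arm.** Take 12 events in 240 participants: 12/240 = 5%. A split of 4/4/4 gives 4/80 = 5% in each arm. A split of 12/0/0 gives 12/80 = 15% in one arm and none in the others. The pooled table is the same.

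**3. Illustration of lost sensitivity.** The 80 per arm (240 in total) is the planned number of completers. All AE rates are assumptions. The background rate p0 is taken as known, and one arm has the raised rate p1. A signal is a count whose one-sided binomial tail under p0 is at most 0.05.

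- Pooled threshold: smallest R with P(Bin(240, p0) ≥ R) ≤ 0.05. Detection: P(Bin(160, p0) + Bin(80, p1) ≥ R).
- By-arm threshold, raised arm named in advance: smallest r with P(Bin(80, p0) ≥ r) ≤ 0.05. Detection: P(Bin(80, p1) ≥ r).
- By-arm threshold when all three arms are scanned: the same with 0.05/3 = 0.0167 in place of 0.05.

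| p0, p1 | R of 240 | r of 80 | Pooled | By arm, named in advance | By arm, three scanned (threshold) |
|---|---|---|---|---|---|
| 2%, 6% | 10 | 5 | 28% | 53% | 35% (6) |
| 5%, 10% | 19 | 8 | 25% | 55% | 28% (10) |
| 5%, 15% | 19 | 8 | 63% | 93% | 78% (10) |
| 10%, 20% | 33 | 14 | 45% | 75% | 65% (15) |

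In the last row the pooled rate is (10% + 10% + 20%)/3 = 13.3%. If all three arms shared that 13.3%, the pooled check would signal with the same probability, 45%. Even a positive pooled signal therefore does not separate one harmful arm from a general excess.

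**4. If the background is not known.** The pooled check then has nothing to be compared with. A by-arm comparison still works: 16/80 against 16/160 gives a two-sided Fisher p = 0.043. At 10%, 10% and 20%, with the raised arm compared against the other two, detection is 61% one-sided or 52% two-sided. These two figures should not be set against the 45%, which assumes a known background.

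**The case against.** A reader might infer that the DSMC sees nothing but pooled counts and that criterion (1) cannot work at all. The documents do not support that, for four reasons.

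- The DSMC also receives event-level records and listings. They lack an arm label but are more than totals.
- The chair is contacted when an SAE is discovered. That sentence in 3e is not limited to related or unanticipated events, although the formal reporting rules in 3e and the review table in 3f are narrower. It is therefore not established that SAEs judged unrelated or anticipated reach the committee only in pooled form, and a narrative may reveal the arm.
- Section 3h does not assign criterion (1) to the DSMC, and 3l envisages suspension by an IRB, the DSMC or an investigator.
- People who know the arm collect safety information. Group leaders and some staff are unblinded (blinding table in D6v). Under the Treatment heading of section 2, session forms are used to pick up possible adverse events, which are escalated, and the Co-PIs review problems with the clinicians. The Co-PIs may consult the DSMC chair (3j).

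It can also be said that pooled reporting protects the blind in a low-risk behavioural trial, where the listed risks are mostly mild or temporary.

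All of this stands as a limit on the point. None of it supplies a comparison of rates between arms. The case-by-case routes depend on someone noticing, and the chair's SAE consultation does not cover non-serious events. A closed report protects the blind as well as a pooled one does, provided it stays with the DSMC.

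**Conclusion.** Sections 3h and 3k need to be reconciled. The criterion is about one intervention, while the only designated monitoring committee (3i) has no documented means of comparing AE rates between arms. An arm-specific excess can still come to light through SAE consultation or through unblinded clinicians and staff, but only case by case.

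That conclusion rests on the text alone. The size is illustrative: about 45% detection pooled against 75% in the affected arm, with rates of 10%, 10% and 20%, 80 per arm, a known 10% background, a one-sided 5% test and the raised arm named in advance. Allowing for a scan of all three arms lowers the 75% to 65%, and in the 5% against 10% scenario the detection advantage almost disappears (28% against 25%). The inability to identify the arm from pooled data holds in every scenario. Full arm size is reached only at the end of the trial, so detection at earlier reviews would be lower on either basis.

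Given the modest risks described, this should be corrected, but it does not undermine the trial.

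**What to change.** - **3k:** keep the open reports to investigators aggregate. Add a closed report, for the DSMC only, tabulating AEs and SAEs by masked arm code (A/B/C) with the number of participants per arm. State that the DSMC may request unmasking.
- **Preparer:** name someone other than the staff member who randomises, because D6l requires that person to have no access to study data during enrolment. Suitable choices are the unblinded staff who already handle treatment data (D6n and the blinding table in D6v), or the DSMC biostatistician working from a coded assignment list.
- **3h:** state who applies criterion (1) and how arm information reaches them. No threshold is proposed here.
- **3j:** add a short closed session without the Co-PIs to the annual review, since the text now has them meet jointly with the DSMC.

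The cost is small: a few sentences, one additional table split, and a closed-report pathway and session to protect the blind. No new data collection is needed, since assignments and event records already exist.

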Hypnotic and Relaxation Exercise		X															
Baseline Data and Demographic Form		X															
Pain Intensity (Primary Outcome)			X			X			X			X			X	X	X
Secondary Outcomes (e.g. Depression, Anxiety)			X			X			X			X			X	X	X
EEG Data (Mediators: Biological)			X												X		
Mediators: Psychological (e.g. Pain Acceptance, Catastrophizing)			X			X			X			X			X	X	X
Pain Intensity, Comfort Levels				X	X		X	X		X	X		X	X			
Treatment Homework Completion				X	X		X	X		X	X		X	X			
Participant Engagement				X	X		X	X		X	X		X	X			
Adverse Events				X	X	X	X	X	X	X	X	X	X	X	X		

* Onset of both enrollment and pre-treatment relative to the onset of treatment may vary given the timing of group sessions
